96 to liraglutide or glargine with or without oral agents at hospital discharge.
97

98 **Endpoints:**

99 **Study Outcomes:**

100 The primary outcome of the study is to determine differences in HbA1c concentration at 26
101 weeks from discharge between liraglutide and glargine insulin therapy.
102

103 The secondary outcome is to compare differences between treatment groups in any of the
104 following measures during the 26 weeks following hospital discharge in patients with T2D:

- 105 • Self-measured blood glucose (SMBG) 7-point profiles
- 106 • Fasting and postprandial BG concentration
- 107 • Incidence rate and number of hypoglycemic events (<70 mg/dl) and severe hypoglycemic
108 events (<40 mg/dl).
- 109 • Percent of patients with 26 week HbA1c $<7.0\%$ and no hypoglycemia
- 110 • Percent of patients with 26 week HbA1c $<7.0\%$ and no weight gain
- 111 • Percent of patients with 12 week HbA1c $<7.0\%$ and no hypoglycemia
- 112 • Change in body weight and BMI

- 113 • Cardiovascular risk factors including changes in blood pressure, heart rate, and lipid
- 114 profile.
- 115 • Total daily dose of insulin
- 116 • Number of emergency room visits and hospital readmissions
- 117 • Acute renal failure during the 26-week follow-up defined as a clinical diagnosis of acute
- 118 renal failure with documented new-onset abnormal renal function (increment in
- 119 creatinine ≥ 0.5 mg/dL from baseline)

120
121

122 **Study type:**

123 The trial is a 26-week, randomized, open label-controlled two-armed, multi-center, multi-
124 national trial investigating the efficacy and safety of liraglutide versus glargine insulin in
125 medicine and surgical patients with T2D after hospital discharge.

126 We will recruit a total of 330 poorly controlled (HbA1c $\geq 7\%$ -10%) patients with T2D treated
127 with diet or oral antidiabetic agents (OAD) or on low-dose insulin therapy (TDD ≤ 0.4
128 unit/kg/day) prior to admission. Patients will be treated with a standard basal bolus insulin
129 regimen during the hospital stay. Prior to hospital discharge, patients will be randomized to
130 liraglutide or glargine with or without oral antidiabetic drugs. After discharge, a member of the
131 diabetes research team will contact patients via telephone call every 2 weeks to assess response
132 to therapy. In addition, patients will be asked to attend an outpatient clinic visit at 2 (optional), 4,

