255 regimen with weekly increments of 0.6 mg until the maintenance dose of 1.8 mg is reached.
256 Liraglutide will be administered once daily by s.c. injections, either in the abdomen, thigh or
257 upper arm. Injections can be done at any time of the day and irrespective of meals. It is
258 recommended that the time of injection is consistent throughout the trial. Subjects will be
259 instructed to perform an air shot before the first use of a new prefilled pen.
260

261 **GROUP 2. Glargine Group**

262

263 **V.e. Treatment recommendations at discharge:**

264

265 **▪ Patients receiving no Therapy prior to admission:**

- 266 • Discharge on glargine once daily at 50% of total hospital dose
 - 267 • Add metformin if A1C \geq 8% and no contraindications.
- 268

269 **▪ Patients receiving OAD prior to admission:**

270

271

272

- If no contraindication, restart pre-admission OADs according to standard of care and investigator’s medical discretion (metformin, sulfonylureas, repaglinide, nateglinide, pioglitazone) in combination to glargine at 50% of hospital dose.
- The total daily dose of insulin secretagogues (sulfonylureas, nateglinides and repaglinide) will be reduced to 50% of pre-admission dose to avoid risk of hypoglycemia.
- DPP4-inhibitors will not be used in combination with liraglutide during the study period

Algorithm for outpatient glargine insulin dose adjustment:

Insulin Glargine	
If mean FBG > 180 mg/dL for the last 2 consecutive days and no episodes of hypoglycemia (BG <70 mg/dL)	Increase daily dose by 4 IU
If mean FBG > 140 mg/dL for the last 2 consecutive days and no episodes of hypoglycemia (BG <70 mg/dL)	Increase daily dose by 2 IU
If mean FBG between 100 to 140 mg/dL for the last 2 consecutive days and no episodes of hypoglycemia (BG <70 mg/dL)	No Change
If any FBG between 70 – 99 mg/dl	Decrease by 4 IU or 10% of total daily dose
If any FBG or RBG < 70 mg/dl	Decrease by 8 IU or 20% of total daily dose
If any FBG or RBG < 40 mg/dl	Decrease total daily dose by 30%

In hospital Diabetes Education. Prior to discharge, participants will be trained on:

1. Diabetes education if not received within 1 year of admission.
2. ADA targets for fasting and premeal BG between 70 to 130 mg/dL.
3. Use of glucose meters for home glucose self-monitoring (meters may vary at different institutions).
4. Keeping BG records, and will receive a log-book to record glucose tests results.
5. Hypoglycemia recognition and management (see VI.B.)

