405
406
407
408
409
410
411
412
413
414
415
416
417
418
419

Potential Risks to the Subjects:

Hypoglycemia. It is possible that following the proposed protocol, patients receiving basal insulin or liraglutide may develop hypoglycemia. For the purpose of this analysis we **symptomatic hypoglycemia** is defined as an event with typical symptoms (i.e., sweating, palpitation, and feeling of hunger) with or without confirmation by plasma glucose <70 mg/dl (3.9 mmol/L). We expect that approximately 20% to 40% of subjects treated with basal insulin alone or in combination to OADs will experience one or more episodes of hypoglycemia during follow-up. We anticipate that less than 10% of patients taking liraglutide alone or in combination to OADs will experience hypoglycemic events.

Severe hypoglycemia is defined as episodes necessitating assistance and associated with measured plasma glucose < 40 mg/dl (2.2 mmol/L) or with prompt recovery after administration of carbohydrates, glucagon, or other resuscitative actions. These episodes may be associated with sufficient neuroglycopenia to induce seizure or coma. Blood glucose measurements may not be available during such an event, but neurological recovery attributable to the restoration of BG to normal is considered sufficient evidence that the event was induced by low plasma glucose. We anticipate that less than 5% of patients on insulin or liraglutide alone or in combination to OADs will experience severe hypoglycemic events.

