Gastrointestinal side effects including nausea and vomiting are more common in patients treated with liraglutide compared to placebo. The frequency of nausea and vomiting is reported in up to 14% of patients receiving higher doses of liraglutide 1.8 mg in combination to metformin and sulfonylurea therapy compared to 3.5% in patients receiving placebo plus OADs (Victoza package insert). The number of adverse events will be collected at each telephone contact or clinic visit. There have been few reported events of acute pancreatitis. Subjects should be informed of the characteristic symptoms of acute pancreatitis: persistent, severe abdominal pain. If pancreatitis is suspected, liraglutide and other potentially suspect medicinal products should be discontinued. If the investigator suspects acute pancreatitis, all suspected drugs should be discontinued until confirmatory test have been conducted and appropriate treatment should be initiated. Subjects diagnosed with acute pancreatitis (as a minimum 2 of 3: characteristic abdominal pain, amylase and/or lipase >3xUNR or characteristic findings on CT scan/ MRI should be withdrawn from the study.

Protection against Risks:

We will follow safeguards to minimize the risk to our subjects: a) we will carefully monitor response to medical treatment every 2 weeks by telephone contact and every 3 months during clinic visits, b) women of reproductive age who are sexually active will undergo a urine pregnancy tests prior to participation in the study, c) female subjects whom are pregnant, breast-feeding, or not willing to use appropriate contraception at time of enrollment will not be included in the study, d) patients with significant comorbidities such as chronic kidney disease

420 greater than stage III, liver cirrhosis, gastroparesis, and pancreatic disorders will be excluded
421 from the study.

422
423 Hypoglycemia: Patients will receive diabetes education prior to discharge and will be instructed
424 on hypoglycemia sign/symptoms and treatment. Patients will be asked to call the diabetes center
425 and/or PCP in the event of hypoglycemia. If a patient develops hypoglycemia, the dose of OAD
426 will be reduced or discontinued and the daily dose of basal insulin will be reduced by 10% to
427 30% (see treatment algorithm).

428 Gastrointestinal side effects including nausea and vomiting may be expected, more commonly in

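### Below 26.7 IU/day the glargine table permits a larger cut for BG <70 than for BG <40; an FBG of 70-99 can meet opposing rows; and the Flow Chart omits dose adjustment at five contacts where the text provides it.

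*Combined protocol and SAP*

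**What the plan says.** The table headed Algorithm for outpatient glargine insulin dose adjustment has six rows.

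- Three rows depend on the mean fasting glucose (FBG) of the last two days: +4 IU above 180 mg/dL, +2 IU above 140, and no change from 100 to 140 ("If mean FBG between 100 to 140 mg/dL for the last 2 consecutive days"). Each also requires that there was no BG below 70.
- Three rows depend on any single value. For an FBG of 70-99: "Decrease by 4 IU or 10% of total daily dose". For any fasting or random value below 70: "Decrease by 8 IU or 20% of total daily dose". For any value below 40: "Decrease total daily dose by 30" per cent, with no unit alternative.

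No rule selects between units and percentage, and the single-value rows have no look-back window.

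Protection against Risks says that after hypoglycemia "the daily dose of basal insulin will be reduced by 10% to" 30%, and refers to the algorithm. It also says "Patients will be asked to call the diabetes center" or their primary care physician after such an event.

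Study type and Follow-up Care provide for insulin dose recommendations at each telephone contact and clinic visit, given by a licensed physician. The dose-adjustment row of the Flow Chart is marked at weeks 2, 4, 6, 8, 12, 18, 22 and 26 only.

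**The concern.** A dose-reduction table should give a larger cut for a more severe event. Here the row for the most dangerous readings can be the weaker one at low doses, because a fixed 8 IU is a large share of a small dose and 30% is not. Other readings fall under two rows that point in opposite directions. Sites in two countries apply the table, so different readings of it would mean different dosing of the comparator.

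What is at stake is first a patient-safety instruction. Beyond that, the size of the cut after a first event bears on repeat events, and Study Outcomes lists "Incidence rate and number of hypoglycemic events" and the total daily insulin dose as secondary measures. This table sets that dose in the glargine arm.

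**Working it through.** **Inputs.** Cuts of 4 IU or 10% (FBG 70-99), 8 IU or 20% (<70) and 30% (<40) come from the algorithm table. The group size of 140 and the assumed hypoglycemia rate of 20-35% come from Sample Size and Power Calculations. The severe-event figure comes from Potential Risks to the Subjects. The plan states no figure of its own to reproduce on this point.

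**1. Order of the cuts.** The 8 IU option equals the <40 cut when 8 = 0.30 x dose, so dose = 8/0.30 = 26.7 IU/day. Below that, 8 IU is the larger.

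| Dose (IU/day) | <70, unit option | <70, 20% option | <40, 30% | Unit option inverts? |
|---|---|---|---|---|
| 12 | 8 | 2.4 | 3.6 | yes |
| 20 | 8 | 4 | 6 | yes |
| 30 | 8 | 6 | 9 | no |
| 40 | 8 | 8 | 12 | no |

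The 20% option never inverts. A second inversion needs units in one row and percentage in the next: 4 = 0.20 x dose gives 20 IU/day, below which 4 IU for FBG 70-99 exceeds 20% for BG <70.

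**2. Against the narrative range.** The condition for inversion (8 IU above 30% of dose) is also the condition for leaving the 10% to 30% range. At 20 IU, 8/20 = 40%. At the lower end, 10% appears in the table only for FBG 70-99, which is not hypoglycemia under the plan's <70 threshold.

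**3. Who could be affected.** Glargine starts at 50% of the hospital dose, so a hospital dose below 26.67/0.50 = 53.3 IU/day means a start below the crossover. The documents give no dose distribution. As an assumption, hospital doses of 30-70 IU/day would give starting doses of 15-35 IU, on both sides of it. The planned 20-35% rate sends 0.20 x 140 = 28 to 0.35 x 140 = 49 glargine patients to the <70 row at least once. For the <40 row the nearest planning figure is severe hypoglycemia ("We anticipate that less than 5% of patients on insulin or liraglutide alone" or with oral agents): 0.05 x 140 = 7, so fewer than 7. Only those below 26.7 IU/day could meet the main inversion.

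**4. Opposing rows.** FBG 95 and 110: mean (95 + 110)/2 = 102.5, no value below 70, so both no change and a decrease apply. FBG 95 and 190: mean (95 + 190)/2 = 142.5, so both +2 IU and a decrease apply. One FBG of 70-99 with a two-day mean of at least 100 is enough. A reading of 35 formally meets both the <70 and <40 rows.

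**5. Chart against text.** The dose-adjustment row has 14 cells for weeks 0 to 26. After baseline the blanks are weeks 10, 14, 16, 20 and 24, all telephone contacts. That is 5 of 12 contacts before week 26, or 5 of 13 including week 26. The longest interval between marks is 6 weeks (12 to 18), against 2 weeks in the text.

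**The case against.** The strongest reply is that Protection against Risks already caps the cut. If 10% to 30% binds, 8 IU is unavailable below 26.7 IU/day and the order cannot reverse. This partly stands: the range is the only text that bounds the 8 IU option, and it should not simply be deleted. But it refers back to the table, which lists 8 IU without limit, so the two conflict and a reader of the table alone would not know of the cap.

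Second, a reader might infer that the table has no order of precedence at all. That goes too far. All three mean-based rows exclude BG <70, so the <70 and <40 rows already override them. Precedence is missing only for FBG 70-99 and, formally, for <40 within <70, where most physicians would apply the more specific row.

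Third, a licensed physician gives each recommendation and may choose the percentage, or apply 8 IU to a reading of 35 because it is also below 70. This is true and makes the inversion avoidable, but it does not make the written rule sound.

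Fourth, a reader might infer from the chart that five contacts pass without dose adjustment. The documents do not support that: the text provides advice at every contact, and patients are asked to call after hypoglycemia. It is a conflict between chart and text that mainly touches scheduled titration.

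**Conclusion.** The point holds as a defect in the written dosing rules that should be corrected. Below 26.7 IU/day the table permits, but does not prescribe, a smaller cut for BG <40 than for BG <70. The number of patients who could meet this is an unknown subset of fewer than 7 of 140, taking the severe-hypoglycemia figure as a stand-in for readings below 40. The 28-49 patients expected to reach the <70 row do not measure the inversion. The FBG 70-99 overlap is easier to trigger, since those values lie within the 70-130 mg/dL fasting target taught before discharge.

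A reader might infer bias in the main comparisons. The documents do not show it. A cut made after a first BG <70 cannot change whether that patient had at least one episode, which is the powered hypoglycemia comparison. The 70-99 overlap could in principle alter the dose before a first event, but nothing in the documents allows its size or direction to be estimated. No effect on HbA1c is shown.

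**What to change.** (a) Make the cut rise with severity at every dose, using the same option (units or percentage) in the 70-99 and <70 rows; the first cut is then always half the second. Then do one of two things: use the percentages (10%, 20%, 30%) below 26.7 IU/day, which agrees with the narrative ceiling; or set the <40 row to 30% or the cut that applies for BG <70, whichever is greater. The floor keeps the order under any reading of the alternatives. With the unit option, however, it gives 8 of 12 IU, or 67%, and so breaks the 30% ceiling. That is a reason to prefer percentages at low doses.

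(b) State that the <40 row governs over the <70 row, and that an FBG of 70-99 within the same two-day window overrides the mean-based rows. Do not extend this to all readings since the last contact: one FBG of 99 twelve days earlier would then force a cut despite a current mean above 180. Under-dosing glargine would favor liraglutide in a non-inferiority comparison.

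(c) In Protection against Risks, keep an upper bound but align the range with the <70 and <40 rows: 20% to 30%. If units are kept at higher doses, note that 8 IU falls below 20% above 8/0.20 = 40 IU/day.

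(d) In the Flow Chart, mark dose adjustment at weeks 10, 14, 16, 20 and 24.

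The cost is a slightly longer table, one revised sentence and five chart cells, with no added visits, data or analyses. The downside is slightly less physician discretion and, if the floor is used with units, larger proportional cuts at low doses, which may raise glucose afterwards.

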175 combination therapy (excluding GLP1 receptor agonists) or on low-dose insulin therapy
176 (TDD ≤ 0.4 unit/kg/day) prior to admission.
- 177 4. Subjects with a hospital admission BG < 400 mg/dL without laboratory evidence of diabetic
178 ketoacidosis (serum bicarbonate < 18 mEq/L or positive serum or urinary ketones).
- 179 5. BMI > 25 Kg/m² and ≤ 45 Kg/m²

181 **Exclusion Criteria**

- 182 1. Age < 18 or > 80 years.
- 183 2. Subjects with stress hyperglycemia (BG > 140 mg/dL and HbA1c < 6.5%)
- 184 3. Subjects with a history of type 1 diabetes (1).
- 185 4. Treatment with GLP1 analogs during the past 3 months prior to admission.
- 186 5. Recurrent severe hypoglycemia or hypoglycemic unawareness.
- 187 6. Subjects with gastrointestinal obstruction, gastroparesis or those expected to require
188 gastrointestinal suction.
- 189 7. History of medullary thyroid cancer or multiple endocrine neoplasias
- 190 8. Patients with acute or chronic pancreatitis, pancreatic cancer or gallbladder disease.
- 191 9. Patients with clinically significant hepatic disease (cirrhosis, jaundice, end-stage liver
192 disease, portal hypertension) and elevated ALT and AST > 3 times upper limit of normal, or
193 significantly impaired renal function (GFR < 30 ml/min).

- 194 10. Treatment with oral or injectable corticosteroid (equivalent or higher than prednisone
195 5mg/day), parenteral nutrition and immunosuppressive treatment.
196 11. Mental condition rendering the subject unable to understand the nature, scope, and possible
197 consequences of the study.
198 12. Female subjects who are pregnant or breast-feeding at time of enrollment into the study.
199 13. Females of childbearing potential who are not using adequate contraceptive methods (as
200 required by local law or practice).

201

202 **Investigational drugs.**

203

- 204 • Liraglutide 6.0 mg/mL solution for subcutaneous (s.c.) injection. The solution will be
205 provided in 3 mL prefilled pen.
- 206 • Liraglutide will be provided to patients
- 207 • Glargine will be provided

208

209

210 **Withdrawal Criteria**

211

- 211 1. The subject may withdraw at will at any time.
- 212 2. The subject may be withdrawn from the trial at the discretion of the investigator due to a
213 safety concern or if judged non-compliant with trial procedures or included in contravention
214 to the inclusion and/or exclusion criteria.
- 215 3. Subject diagnosed with acute pancreatitis by clinical and/or radiographic criteria.

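### Glargine dose table: below about 26.7 IU/day the fixed 8 IU option for a reading under 70 mg/dl is larger than the cut for a reading under 40 mg/dl, and falls outside the 10% to 30% range in the safety text

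*Combined protocol and SAP*

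**What the plan says.** The protocol's table headed Algorithm for outpatient glargine insulin dose adjustment has three decrease rows:

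- The mildest row covers fasting glucose from 70 up to 99 mg/dl. Its instruction is "Decrease by 4 IU or 10% of total daily dose".
- The middle row covers every fasting or random value under 70 mg/dl. Its instruction is "Decrease by 8 IU or 20% of total daily dose".
- The most severe row covers every fasting or random value under 40 mg/dl. Its instruction is "Decrease total daily dose by 30" (a percentage), and it has no fixed-unit option.

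Nothing in the table or the surrounding text says whether the larger or the smaller option applies, or whether the choice is left to the physician. No dose is given below which the fixed-unit option stops applying. The under-70 row has no lower bound, so a reading below 40 meets both of the last two conditions.

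The Protection against Risks section, in its paragraph on hypoglycemia, says that "the daily dose of basal insulin will be reduced by 10% to" an upper end of 30%, and refers the reader to the treatment algorithm.

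The discharge recommendations for the glargine group set the starting dose as a fraction of the inpatient dose: "Discharge on glargine once daily at 50% of total hospital dose" for patients on no prior therapy, and the same fraction for patients on oral agents. No inpatient dose is given in IU or IU/kg.

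**The concern.** A dose-reduction table should give one answer for one patient and should respond at least as strongly to a worse reading. Here two of the three decrease rows offer a fixed number of units or a percentage, and the most severe row offers a percentage only. A fixed number of units is a growing share of the dose as the dose falls, so at low doses the 8 IU option must at some point overtake the 30% cut.

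Two things are at stake. The first is consistency: two physicians who both follow the table can make different cuts for the same patient, in an open-label multicenter trial where titration of the comparator matters. The second is coherence of the safety text, because a cut that the table permits can fall outside the range that the risk section attributes to that table.

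**Working it through.** The plan states no crossover dose, so there is no figure of its own to reproduce. The check is arithmetic on the table. Let D be the current glargine dose in IU/day.

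**Inputs from the algorithm table:** 4 IU or 10% (70–99 mg/dl); 8 IU or 20% (<70 mg/dl); 30% (<40 mg/dl). **From Protection against Risks:** a range of 10% to 30%.

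**Step 1. Where the options within a row agree.** 4/0.10 = 40 IU and 8/0.20 = 40 IU. Below 40 IU/day the fixed-unit cut is the larger; above it the percentage cut is the larger.

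**Step 2. Where the 8 IU option overtakes the 30% cut.** 8 > 0.30 × D when D < 8/0.30 = 26.7 IU/day.

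| D (IU/day) | <70 row, IU option | <70 row, 20% option | <40 row, 30% |
|---|---|---|---|
| 16 | 8 IU = 50.0% | 3.2 IU | 4.8 IU |
| 20 | 8 IU = 40.0% | 4.0 IU | 6.0 IU |
| 24 | 8 IU = 33.3% | 4.8 IU | 7.2 IU |
| 26 | 8 IU = 30.8% | 5.2 IU | 7.8 IU |
| 27 | 8 IU = 29.6% | 5.4 IU | 8.1 IU |
| 40 | 8 IU = 20.0% | 8.0 IU | 12.0 IU |

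The order is reversed at 26 IU and below, and correct at 27 IU and above.

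**Step 3. Comparison with the risk section.** The 8 IU option exceeds 30% of the dose at exactly the same point, D < 26.7 IU/day. The percentage options (10%, 20%, 30%) stay within the stated range at every dose and rise with severity.

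**Step 4. Spread between two compliant physicians in the <70 row.** The ratio is 8/(0.20 × D). It exceeds 2 when D < 8/(0.20 × 2) = 20 IU/day. At 25 IU/day it is 8/5 = 1.6.

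**Step 5. Are such doses plausible?** The documents give no hospital dose, so a range is assumed. With a hospital total of h unit/kg/day and a 50% start, the starting dose is below 26.67 IU when body weight is below 26.67/(0.5 × h).

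| Assumed h (unit/kg/day) | Starting dose below 26.7 IU for weight under |
|---|---|
| 0.3 | 26.67/0.15 = 178 kg |
| 0.4 | 26.67/0.20 = 133 kg |
| 0.5 | 26.67/0.25 = 107 kg |
| 0.6 | 26.67/0.30 = 89 kg |
| 0.8 | 26.67/0.40 = 67 kg |

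Affected doses are plausible over much of this range and less so at its upper end. How many patients would be at such doses when a low reading occurs cannot be derived.

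**The case against.** The best defense is that the table is meant to be read with the risk section. Its percentages are 10, 20 and 30, which match the stated range and keep the right order at every dose. That stands as a coherent reading. It does not remove the conflict, because the table offers 8 IU on equal terms and nothing restricts its use.

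A second defense is that a reading below 40 also meets the under-70 condition, so the 8 IU row might apply to it too. The reversal does need the 30% row alone to govern such readings. That is the natural reading, but the table does not say so, and this is a further reason to clarify it.

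Third, the Follow-up Care section has a licensed physician make these adjustments as recommendations. Judgment may soften the effect in practice; it does not settle what the table means.

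Four stronger readings are tempting, and the documents do not support them:

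- *A second reversal, with 4 IU at 70–99 mg/dl exceeding 20% at <70 mg/dl when the dose is below 20 IU/day.* This arises only if units are used in one row and percentages in the next. With either measure used consistently, those two rows stay in order.
- *The plan itself puts patients at about 18 IU/day* (90 kg × 0.4 unit/kg/day × 50%). The 0.4 figure is a ceiling on insulin before admission ("TDD ≤ 0.4 unit/kg/day) prior to admission"), not a hospital dose. The 50% start is written for patients on no therapy or on oral agents, and no body weight is given.
- *A wrong choice costs 8 weeks of recovery against 4.* At 18 IU/day, regaining 8 IU at +2 IU takes 4 steps, against 2 for 3.6 IU (20%). At +4 IU, which the table gives for a mean fasting glucose above 180 mg/dl, it takes 2 against 1. The interval between steps is also uncertain: the text speaks of every contact, while the flow chart marks dose adjustment at weeks 2, 4, 6, 8, 12, 18, 22 and 26. This is one scenario among several.
- *Glargine is under-titrated, so non-inferiority becomes easier to show.* No HbA1c effect can be computed from the documents. Larger cuts could also reduce hypoglycemia on glargine, which would work against the expected advantage of liraglutide on the secondary outcome of major interest.

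**Conclusion.** Wrong as written, in a narrow sense. The 8 IU option conflicts with the 30% row, and with the 10% to 30% statement in the risk section, at every dose below 26.7 IU/day. The reversal rests on two conditions: the 8 IU option is chosen, which the table permits, and the under-40 row alone governs readings below 40. The conflict with the risk section needs only the first.

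The consequence is that compliant physicians can make different cuts for the same patient, more than twofold apart only below 20 IU/day, and that the more severe reading can draw the smaller response. The frequency is unknown, and neither the size nor the direction of any effect on the trial's comparisons can be established from the documents.

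**What to change.** The sponsor should reconcile the decrease rows of the glargine algorithm with each other and with the range in Protection against Risks, so that the fixed-unit and percentage options do not conflict at the doses expected in this population. The table should also state which row governs a reading below 40 mg/dl that also meets the under-70 condition. The values are for the clinical lead to decide; none is proposed here.

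The cost is a revised table, a matching edit to the risk section if needed, and a memo to sites. No extra visits or measurements follow. The downside is that sites lose the free choice between units and percent.
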